5.2.5 Rules for imputing other adverse event data

If the assessment of the intensity is missing, the most severe case will be assumed in the frequency tables of adverse event intensity.

If the assessment of the relationship to the Sculptra® Aesthetic or injection procedure is missing, a possible relationship to the Sculptra® Aesthetic will be assumed in the frequency tables of possibly related adverse events.

5.3 Relative Day Ranges and Visit Windows

If a subject discontinues early, the efficacy data (wrinkle assessments and investigator/subject global evaluations) from Visit 12 (Year 5) will be reassigned to a scheduled visit based on the relative ranges in the following table. If a result already exists for the calculated visit or the calculated visit was not a scheduled visit, the next scheduled visit will be assigned.

Relative day calculations will be the parameter visit date of interest minus the Study First Treatment Date plus one.

Table 1: Visit Collection Time and Relative Day Ranges

Collection Time (Target Day ± Visit Window)	Relative Day Ranges
Baseline (Day 1)	≤ Day 1
Week 3 (Day 22 ± 3 days)	Day 2 to Day 32
Week 6 (Day 43 ± 3 days)	Day 33 to Day 53
Week 9 (Day 64 ± 3 days)	Day 54 to Day 124
Month 6 (Day 184 ± 2 weeks)	Day 125 to Day 290
Month 13 (Day 397 ± 2 weeks)	Day 291 to Day 564
Year 2 (Day 731 ± 4 weeks)	Day 565 to Day 913
Year 3 (Day 1096 ± 4 weeks)	Day 914 to Day 1278
Year 4 (Day 1461 ± 4 weeks)	Day 1279 to Day 1643
Year 5 (Day 1826 ± 4 weeks)	≥ Day 1644

5.4 Calculation of Duration and Time to Onset:

Below are the rules on how duration and time to onset are calculated:

- 1. Duration = Event End Date Event Start Date + 1
 - For events that are ongoing, the formula will be updated per following scenarios:
 - a. If the subject had XXX visit, duration will be XXX visit date minus start date plus 1;
 - b. If the subject discontinued the study, duration will be discontinuation date minus event start date plus 1;

- c. If none of the above, the event's duration will be time of visit minus study day of event start date plus 1, where time of visit is defined as scheduled study day + 4 weeks (2 weeks for Month 13).
- 2. Time to Onset (from treatment) = Event Start Date Date of First Treatment.

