2.3 Interim Analyses

Interim analyses are planned following completion of all subjects' Month 13, Year 2, 3, and 4 follow-up visits. All safety and efficacy data up to the interim cut-off date will be cleaned, interim locked, analyzed and reported.

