4.4.6 Interim analyses

Interim analyses will be conducted on all study variables at 4 time points:

- Following completion of all subjects Month 13 follow-up visits;
- Following completion of all subjects Year 2 follow-up visits;
- Following completion of all subjects Year 3 follow-up visits; and
- Following completion of all subjects Year 4 follow-up visits.

For these interim analyses, AEs and concomitant medications that started on or before the study visit will be included. If the study visit was not conducted, events/medications that started on or before the scheduled study day + 4 weeks (2 weeks for Month 13) will be included.

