5.2 Missing Data

5.2.1 Missing AEI data due to subject discontinuation

If a subject discontinues the study before 2 or 5 years without an adverse event of interest, the subject will be assumed to have no adverse events of interest between the date of discontinuation and the 2 or 5-year time point when conducting the formal hypothesis testing. A sensitivity analysis will be conducted using the multiple imputation method to impute an outcome for these subjects.

To better determine covariates that will be used to conduct multiple imputation for missing event, the subjects who remain in the study or have had an event of interest will be compared to those who drop out without any injection site nodules and/or papules (or any AEI other than injection site nodules and/or papules), with respect to baseline characteristics and number of injection sessions to assess if missing appears to be missing at random or missing completely at random. Baseline characteristics include demographics (age, gender, ethnicity and race), Fitzpatrick skin type and medical history. Continuous factors include age and number of injection sessions. Age will be compared using a two sample t-test. Number of injection sessions will be compared using a wilcoxon rank sum test, as the data is highly discrete. Categorical factors will be compared using Pearson's Chi-square test, with Fisher's exact test as an alternative when the cell counts are less than 5.

A listing of discontinuation reasons for subjects who discontinued without an injection site nodule and/or papule or any AEI other than injection site nodule and/or papule will be provided, to detail the reason for missing.

5.2.2 Rules for imputing stop dates for adverse event, subject reported event, and prior/concomitant therapy

The imputed stop date will be derived from the CRF event/therapy stop date. If the CRF stop date day, month, and year are not missing then the imputed stop date will equal the CRF stop date. If any part of the CRF stop date is missing, the following rules will be utilized to impute the stop date.

- If the event/therapy is ongoing, the stop date will be set to missing.
- Otherwise, if the year is missing, a) if the subject is still in the study and the study is ongoing, the event will be assumed to be ongoing, and stop date will be set to missing; b) if the subject has left the study, the stop date will be set to the subject's final study date.

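### At an interim look, SAP 5.4 read literally ends a still-present lesion at the subject's visit but lets one that resolved after that visit keep its full duration, and SAP 4.4.4.2 gives a different rule

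*SAP*

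**What the plan says.** SAP 5.4 computes duration as end date minus start date plus one when an event has ended, with no upper limit at the visit. For an ongoing event its first rule is "If the subject had XXX visit, duration will be XXX visit date minus start date plus 1". If there was no visit, the discontinuation date is used. Failing that, the end is the scheduled day plus 4 weeks (plus 2 weeks for Month 13).

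SAP 5.2.2 governs which stop date enters the formula: "If the CRF stop date day, month, and year are not missing then the imputed stop date will equal the CRF stop date". For the rest, "If the event/therapy is ongoing, the stop date will be set to missing". Ongoing is read there from the CRF record and from whether the subject is still in the study, not from status on the day of the interim visit.

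SAP 4.4.6 decides which events enter a look, and it filters on start date: "AEs and concomitant medications that started on or before the study visit will be included". It says nothing about stop dates. A look takes place only after every subject has passed the visit (for example "Following completion of all subjects Year 2 follow-up visits"), and SAP 2.3 states the lock as "All safety and efficacy data up to the interim cut-off date will be cleaned".

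SAP 4.4.4.2 handles ongoing events of interest differently. They are either left out of the duration summary or given the data cutoff date as their end date. The same section splits duration at 30 days and asks for Kaplan-Meier estimates of the maximum duration per subject.

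**The concern.** Because a look waits for the last subject, earlier enrollees have adverse event follow-up beyond their own visit. It comes from the monthly contacts (Protocol 12.2) and from follow-up of events of interest until resolution or stabilization (Protocol 12.3). On the literal text that extra time is used for a lesion that resolved in the interval and thrown away for a lesion that did not. The follow-up horizon then depends on the outcome being measured, and the error runs one way: only unresolved lesions are shortened.

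Duration is a secondary objective (Protocol 5.2, SAP 3.2) and is listed among the secondary safety endpoints in Protocol 13.3.2.1. At stake is whether the interim reports understate persistence, and whether two programmers, one following 5.4 and the other 4.4.4.2, would produce different tables.

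**Working it through.** The plan states no figure on this point, so the rules are applied first to worked cases and then to a simulation.

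**Worked case, Month 13 look.** Two lesions start on Day 380. Both subjects are seen on Day 397, the target day in SAP Table 1. The lock is taken, for illustration, as Day 760.
- Resolved on Day 600, SAP 5.4 with 5.2.2: 600 − 380 + 1 = 221 days.
- Still present, SAP 5.4(a): 397 − 380 + 1 = 18 days, in the class of 30 days or less.
- Still present, SAP 4.4.4.2 with cutoff at the lock: 760 − 380 + 1 = 381 days.

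**Worked case, Year 2 look.** Onset Day 681, visit Day 731. Still present: 731 − 681 + 1 = 51 days. Resolved 60 days after the visit (Day 791): 791 − 681 + 1 = 111 days. With every event cut at the visit, both read 51. With every event followed to the data cut, the resolved one reads 111 and the ongoing one 141, 231 or 416 for an assumed lag of 90, 180 or 365 days. Either consistent rule removes the reversal.

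**Simulation inputs** (Protocol section 4, pivotal study; median and mean in days):
- Nodules: onset 160 and 209, duration 100 and 180.
- Papules: onset 55 and 159, duration 110 and 176.
- Mix 10:12, that is 8 + 2 subjects with nodules and 10 + 2 with papules.
- Lognormal shape assumed, with sigma = √(2 ln(mean/median)): 0.731 and 1.457 for onset, 1.084 and 0.970 for duration.
- Assumed and not in the documents: uniform enrolment over 12 months, so that the lag from visit to lock is uniform over that span. The range tried is 6 to 24 months.

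At Month 13 about 21% of events straddle the visit and about 10% (14% to 6%) are still ongoing at lock. These are recorded at a mean of about 224 days, although about 356 days (295 to 440) had been observed.

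| Month 13 rule | Kaplan-Meier P(duration > 365 d) |
|---|---|
| True value in the model | 0.112 |
| 5.4 dates, ongoing events counted as ended | 0.048 (0.034 to 0.070) |
| 5.4 dates, ongoing events censored | about 0.084 (0.081 to 0.093) |
| One cut at the visit, counted as ended | 0.024 |
| One cut for all events, censored | 0.110 to 0.112 |

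The third and fifth rows differ only in whether there are two cut dates or one, so that gap is the part due to the asymmetry. The drop from 0.112 to 0.048 mixes it with the separate effect of counting unresolved lesions as ended. The fourth row shows that a single cut without censoring does worse still.

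At Year 2 the censored comparison is about 0.109 against 0.112. With no lag the asymmetry has no effect. With nodule inputs alone and lags of up to 180 to 730 days, the censored comparison at Month 13 is 0.055 to 0.087 against about 0.117.

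**The case against.** The best defence is that the plan intends a single cut per subject. SAP 4.4.6 admits events up to the visit, or up to the scheduled day plus its window, and 5.4(a) and (c) use the same limits. If ongoing means ongoing at that visit, a lesion that resolves later is cut there too and the asymmetry disappears. SAP 5.2.2 is a rule for incomplete dates and was not written to settle interim truncation. SAP 2.3 does not say that its cut-off is one calendar date. All this is fair: no sentence states outright that later stop dates are kept. But no sentence caps them either, and 5.2.2 ties ongoing to the CRF record and study status. The single-cut reading is possible but unwritten.

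A second defence is that 4.4.4.2 would exclude the ongoing lesion or end it at data cutoff, so the 18-day value need not arise. That is correct for a programmer who follows 4.4.4.2. On a calendar reading of data cutoff, it also means that the two sections conflict.

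Three stronger readings are tempting and are not supported:
- *Persistent lesions are generally recorded as shorter than resolved ones.* The reversal needs a comparison lesion that resolved between the visit and the lock. Against all resolved events, ongoing ones are still longer on average in the simulation (224 against 127 days at Month 13, 466 against 149 at Year 2).
- *The two cut dates cause the whole fall to 0.048 and all the contamination of the 30-day class.* Much of both comes from counting ongoing events as ended. About 4% of that class are lesions known to have lasted longer, but a common cut at the visit without censoring would fill about 13% of it with lesions not yet ended.
- *The main safety conclusions are at risk.* The co-primary endpoints and the 2-year secondary endpoints in SAP 4.2.2.1 are incidences and do not use duration.

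**Conclusion.** The point holds in a limited form. As written, SAP 5.4(a) can record a lesion that is still present as shorter than one with the same onset that resolved after the visit, and can move it into the class of 30 days or less. It also conflicts with 4.4.4.2 if data cutoff is a calendar date. The part due to the two cut dates is about 0.084 (0.081 to 0.093) against 0.110 to 0.112 for the proportion lasting beyond 365 days at Month 13, and about 0.109 against 0.112 at Year 2. It is essentially absent at the final analysis.

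These sizes rest on lognormal onset and duration taken from the pivotal study and on an enrolment span that the documents do not give, so they are illustrations. The effect is confined to descriptive duration summaries of events of interest at interim looks. Section 5.4 was added in SAP version 2.0 (August 2018), and the documents do not show whether a Month 13 look was still to come.

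**What to change.** In SAP 5.4, define one cut-off per look and apply it to stop dates and ongoing status alike. The better choice is the last adverse event assessment, at a visit or monthly contact, on or before the interim data cut-off, because it uses all the follow-up collected. An event that has not ended by that cut is ongoing, and is censored there in the Kaplan-Meier analysis of duration.

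If a common cut at the visit is preferred, a stop date after the visit must make the event ongoing at the visit, and censoring is then essential. Without it the Month 13 proportion falls to 0.024.

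State whether data cutoff in 4.4.4.2 and the interim cut-off date in 2.3 are the same date, and align 4.4.4.2 with 5.4.

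The cost is a few lines of SAP text and a small programming change. Under the preferred rule interim durations become somewhat longer, so any duration figures already reported under 5.4 would not be directly comparable.

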6.0 Deviations from protocol

The following changes were made to the analyses planned in the protocol.

- Study primary objectives in this SAP were revised compared to those stated in Protocol Section 5.1 to be consistent with the primary endpoints as stated in the co-primary safety endpoints (Protocol Section 13.3.2.1) and primary hypotheses (Protocol Section 13.5.4.1).
- Analysis of duration and time to onset were only provided for the AEIs. These changes were made to clarify inconsistencies in the protocol between section 13.3.2.1 and 13.5.4.2. The SAP follows what is in the protocol section 13.5.4.2.
- PP population based analysis will only be conducted if it is at least 5% different than the ITT population.
- Clarification was made to the description of the groups being compared for determining covariates in the MI model (SAP Section 5.2.1) from what was stated in the protocol Section 13.5.4.1.

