5 STUDY OBJECTIVES

5.1 PRIMARY

The primary objective of the study is to assess the long-term safety of Sculptra® Aesthetic in immune-competent subjects as a single regimen for correction of WAS 2 to 4 NLF contour deficiencies and other facial wrinkles in which deep dermal grid pattern (cross-hatch) injection technique is appropriate, for the following variables:

- The device-related long-term incidence of chronic inflammation (nodules, papules, granulomas, skin necrosis, hypersensitivity, and other injection site reactions) in subjects with Fitzpatrick skin type I-VI.
- The incidence of hypertrophic scarring, keloid formation, and changes in skin pigmentation in subjects with Fitzpatrick skin type IV-VI.

5.2 **SECONDARY**

Secondary objectives include the following:

- To evaluate the time to onset, duration, severity, relationship to Sculptra® Aesthetic and/or injection procedure, and outcome of all adverse events, including adverse events mentioned under the primary objectives, during the course of the study, by Fitzpatrick skin type.
- To evaluate the change in the WAS from baseline to post-treatment follow-up time points at Months 6, 13, and Years 2, 3, 4, and 5 in NLFs and other facial wrinkles.
- To evaluate Investigator/subject global assessments at Months 6, 13, and Years 2, 3, 4, and 5.

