12.1.2 Visit 2 (Week 3) – second treatment, if needed

The following procedures will be performed (listed in recommended order):

- All adverse events will be collected including, but not limited to:
 - Adverse events of interest: nodule, papule, hypertrophic scarring, keloid formation, granuloma (confirmed by a biopsy), changes in skin pigmentation, skin necrosis, hypersensitivity reaction, and unexpected changes in wrinkle contour
 - Adverse events reported in more than 1% of subjects during clinical trials regardless of relationship to the device/procedure: injection-site edema, injection-site tenderness, injection-site erythema, injection-site pain, injection-site bleeding, injection-site itching, injection-site bruising, injection-site inflammation, injection-site discomfort, injection-site infection, injection-site acne, injection-site dermatitis, and injection-site skin dryness; nasopharyngitis, headache, hypertension, fracture, urinary tract infection, tooth abscess, syncope, and cough
 - Adverse events reported in less than 1% of subjects during clinical trials regardless of relationship to the device/procedure: sinusitis, influenza, bronchitis, acrochordon, anxiety, colitis, contusion, corneal abrasion, cyst, depression, dermatitis, eczema, gastritis, herpes simplex, hypercholesterolemia, hypersensitivity, hypothyroidism, injection site desquamation, injection-site rash, lower respiratory infection, lymphadenopathy, migraine, muscle injury, muscle twitching, myalgia, osteoarthritis, osteopenia, rheumatoid arthritis, gastroenteritis, skin burning sensation, spider vein, staphylococcal infection, stress symptoms, tooth infection, toothache, and vaginal infection
 - Adverse events reported during postmarketing surveillance regardless of relationship to the device/procedure: allergic reaction, angioedema (Quincke's edema), application site discharge, fatigue, hypersensitivity reaction, hypertrophy of skin, injection-site abscess, injection-site atrophy, injection-site fat atrophy, injection-site granuloma (including ectropion), injection-site induration, lack of effectiveness, malaise, periorbital nodules, photosensitivity reaction, scar and skin discoloration, skin infection, skin rash, skin roughness, skin sarcoidosis, telangiectasias, and urticarial
- Collect and review the diary card. Record relevant medication use that have occurred since the last visit.

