3.2 Secondary

Secondary objectives include the following:

- To evaluate the time to onset, duration, severity, relationship to Sculptra® Aesthetic and/or injection procedure, and outcome of all adverse events, including adverse events mentioned under the primary objectives, during the course of the study, by Fitzpatrick skin type.
- To evaluate the change in the WAS from baseline to post-treatment follow-up time points at Months 6, 13, and Years 2, 3, 4, and 5 in NLFs and other facial wrinkles.
- To evaluate Investigator/subject global evaluations at Months 6, 13, and Years 2, 3, 4, and 5.

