4.2.2 Safety variables

4.2.2.1 Adverse events

Adverse events (AEs) are defined as adverse events that develop or worsen during the ontreatment period (time from first dose of Sculptra® Aesthetic to the end of the study). All adverse events will be coded using the current version of MedDRA.

The injection site adverse events listed below are defined as **Adverse Events of Interest** (AEI) in this study.

- Injection Site Nodule
- Injection Site Papule
- Hypertrophic scarring
- Keloid formation
- Changes in the skin pigmentation at the site of injection compared to adjacent skin
- Granuloma (confirmed by a biopsy)
- Skin necrosis
- Hypersensitivity reactions
- Unexpected change in wrinkle contour

The co-primary safety endpoints are:

1. The percentage (incidence rate) of subjects with any injection site nodule and/or papule over 5 years.

- 2. The percentage (incidence rate) of subjects with any of the following injection site events over 5 years, and they are termed as AEI other than injection site nodule and/or papule:
 - Hypertrophic scarring
 - Keloid formation
 - Changes in the skin pigmentation at the site of injection compared to adjacent skin
 - Granuloma (confirmed by a biopsy)
 - Skin necrosis
 - Hypersensitivity reactions
 - Unexpected change in wrinkle contour

The secondary safety endpoints are:

- the percentages (incidence rate) of subjects with any injection site nodule and/or papule over 2 years
- the percentages (incidence rate) of subjects who experienced any AEI other than injection site nodule or papule over 2 years

Summaries on Adverse Events and Adverse Events of Interest only take into consideration of those events that are treatment emergent.

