4.4.4 Analysis of safety data

4.4.4.2 Other analyses of adverse events

All adverse events will be collected and summarized with the number of subjects reporting adverse events by number of injections, system organ class, preferred term, severity, relationship to the Sculptra® Aesthetic, and relationship to injection procedure.

For injection site nodules and/or papules and any other AEI, summaries will also include incidence rates by location and intervention, duration (<=30 days versus >30 days), and time to onset (<=30 versus >30 days for nodules and/or papules, and <=120 versus >120 days for any other AEI). Duration and time to onset of all events will also be summarized with descriptive statistics. Kaplan Meier estimates and plots will also be provided to estimate the maximum duration and time to the first occurrence within a subject. Time to onset is defined as the time from first injection to the start of the event.

To obtain duration of injection site nodules and/or papules and any other AEI, events that are ongoing will be handled in two ways: 1) excluding events that are ongoing at the time of data cutoff; and 2) assigning data cutoff date as the event end date.

The following frequency distributions of adverse events (incidence tables) will be provided:

- Overview of adverse events
- All AEs by number of injection sessions
- All AEs by system organ class and preferred term by decreasing frequency
- All AEs by system organ class, preferred term and intensity
- All AEs by system organ class, preferred term and relationship to treatment
- All AEs by system organ class, preferred term and relationship to procedure

The following listings will be provided:

- All adverse events
- Serious adverse events
- Adverse events that lead to discontinuation of Sculptra® Aesthetic
- Adverse events that lead to discontinuation of study
- Injection site nodules and papules
- AEI, other than injection site nodule and papule

The incidence rate of injection site nodule and/or papule will also be summarized by study site and baseline wrinkle assessment.

Subject reported injection related events collected in the diary card will be summarized by frequencies and percentages. Severity of subject reported injection related events after initial treatment session will be summarized by anatomic areas and Fitzpatrick skin type groups.

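### SAP 3.2 asks for onset and duration of all adverse events but SAP 6.0 limits those analyses to the adverse events of interest (AEIs), so no clearly planned table separates late or persistent non-AEI injection-site reactions from transient ones

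*SAP*

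**What the plan says.** SAP 3.2, like Protocol 5.2, sets this secondary objective: "To evaluate the time to onset, duration, severity, relationship to Sculptra® Aesthetic and/or injection procedure, and outcome of all adverse events", to be examined by Fitzpatrick skin type. SAP 6.0 lists a departure from the protocol: "Analysis of duration and time to onset were only provided for the AEIs". The reason given is an inconsistency between Protocol 13.3.2.1, which names duration and onset of adverse events generally among the secondary safety endpoints, and Protocol 13.5.4.2, which plans these analyses for AEIs only. SAP 6.0 follows 13.5.4.2 and does not mention the objective in 3.2.

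The relevant paragraph of SAP 4.4.4.2 opens with the AEIs: "For injection site nodules and/or papules and any other AEI, summaries will also include incidence rates by location and intervention, duration". It then splits duration at 30 days, and onset at 30 days for nodules and papules or 120 days for other AEIs. In the same paragraph it says: "Duration and time to onset of all events will also be summarized with descriptive statistics". The tables listed there for all adverse events cover number of injection sessions, system organ class and preferred term, intensity, and relationship to treatment or procedure. None is by duration or onset. Listings of all adverse events are planned, and diary events are summarised separately.

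Protocol 5.1 counted "nodules, papules, granulomas, skin necrosis, hypersensitivity, and other injection site reactions" as chronic inflammation. SAP 3.1 no longer has the last item of that list, and SAP 6.0 discloses that the primary objectives were revised. SAP 1.0 still gives the long-term incidence of chronic inflammation as a purpose of the study.

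**The concern.** An objective in the current SAP has no clear analysis behind it for events outside the nine AEI terms. The gap touches the purpose of a five-year safety study. For a reaction that many subjects have for a few days after injection, incidence says little about chronicity. Duration or late onset is what distinguishes a lasting reaction from a procedural one.

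At stake is whether the report will contain a pre-planned figure for subjects with late or long-lasting pain, swelling or redness at the injection site, overall and in the darker skin types for which the study was required.

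**Working it through.** **Texts side by side**

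- SAP 3.2: onset and duration, all adverse events, by skin type.
- SAP 6.0: onset and duration, AEIs only.
- SAP 4.4.4.2: all events, inside a paragraph about AEIs. If this means all AEI events, SAP 3.2 is unmet. If it means all adverse events, it contradicts SAP 6.0. Either reading needs a correction; the first is more likely, given the paragraph and 6.0.

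**Inputs** (Protocol section 4, Tables 3 and 4; Protocol 7.1)

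- Injection-site pain, first-session 14-day diary: 82 of 116. Check: 82/116 = 70.7%, as printed.
- Delayed injection-site pain, about 20 months after first injection: 1 of 116. Check: 1/116 = 0.86%, printed as 0.9%; exact 95% interval 0.02% to 4.71%.
- Planned enrolment: 863, with at least 22 of type IV and 122 of types V-VI.

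**What a once-per-subject table would show, if early and late pain shared one preferred term**

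- Late case nested among early cases: 82/116 = 70.7%, unchanged.
- Independent: 0.7069 + 0.0086 − 0.7069 × 0.0086 = 0.709, or 70.9%.
- No overlap, the extreme case: 83/116 = 71.6%.
- Sampling error at n = 863: 1.96 × √(0.7069 × 0.2931 / 863) = 0.030, or ±3.0 points.

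The shift is 0 to 0.9 points against a half-width of 3.0. With assumed late rates of 0.5%, 1%, 2% and 5%, under independence, the table would read 70.8%, 71.0%, 71.3% and 72.2%; the largest shift, 1.5 points, is still inside the half-width.

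**What a split would show, at pivotal rates**

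- Expected early pain: 863 × 82/116 = 610 subjects. Expected late pain: 863 × 1/116 = 7.4, of whom 7.4 × 0.7069 = about 5 would already be counted as early cases.
- Shown separately, 7/863 = 0.8% (exact 95% interval 0.3% to 1.7%).
- By group at the minimum enrolment: 122/116 = about 1 late case in types V-VI, 22/116 = 0.2 in type IV, and (863 − 122 − 22)/116 = 719/116 = about 6 in types I-III. Group figures would be descriptive only.

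**Onset origin**

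SAP 5.4 counts onset from first treatment. A same-day reaction at the third session (Day 43) has onset 43 − 1 = 42 days, and at the fourth (Day 64) 63 days. A 30-day split from first injection would label both late. The 120-day split would not.

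**The case against.** The restriction is declared and follows Protocol 13.5.4.2, so the visible protocol methods contained no wider analysis that the SAP removed. The change to the primary objective is disclosed too. This stands, but SAP 6.0 reconciles two method sections and leaves its own objective in 3.2 untouched.

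The sentence on all events might already supply descriptive statistics for every adverse event. It might, but it then conflicts with 6.0 and has to be clarified.

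A reader might infer that chronic reactions outside the AEI list cannot be identified in this study at all. The documents do not support that. Protocol 9.1.1 has onset and resolution dates on the case report form, and SAP 4.4.4.2 plans a listing of all adverse events. What is missing is a planned summary.

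A reader might also extend the masking argument to "injection-site abscess, injection-site atrophy, injection-site fat atrophy, injection-site granuloma (including ectropion), injection-site induration". That does not follow. Apart from granuloma, which is an AEI when confirmed by biopsy, these are separate terms, named as postmarketing reports and absent from the common diary reactions in Tables 3 and 4, so transient swelling does not swamp their counts. Some may be recorded under the AEI for wrinkle contour, which Protocol 9.1.1 defines broadly enough to take in uneven contour and changes in texture, elasticity or sensation.

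Finally, the pivotal rates come from another study's 14-day diary. Here diary events are reported apart from adverse events, so early pain may not share a table with late pain. Against this, Protocol 12.1.2 also names injection-site pain, edema and erythema among adverse events to collect. The degree of masking is open.

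**Conclusion.** The inconsistency among SAP 3.2, 4.4.4.2 and 6.0 is real and should be corrected. Its practical consequence is limited but relevant: no clearly planned table distinguishes late or persistent non-AEI injection-site reactions from transient ones. The pivotal pain data show that a late rate of 0.9% could sit almost unseen inside an incidence of about 71%.

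This rests on three assumptions: that the pivotal rates are a fair guide, that early and late reactions enter the same incidence table, and that the blacked-out safety analysis sections (Protocol 13.5.4.1 and its SAP counterpart) contain nothing wider. SAP 6.0 makes a wider analysis there unlikely, but this cannot be checked. No count of affected subjects can be predicted for this trial. The information is recoverable from collected data, so this is a cheap improvement to the analysis plan and not a loss of data.

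**What to change.** Amend SAP 4.4.4.2 and 6.0 as follows:

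- Apply the duration split (≤30 versus >30 days) and an onset summary to all injection-site adverse events, overall and by Fitzpatrick group (I-III, IV, V-VI), using the SAP 5.4 rules for ongoing events.
- Say in 4.4.4.2 which events the sentence on all events covers.
- Confine the 6.0 deviation to adverse events not at the injection site, and narrow SAP 3.2 to match.
- State the origin for onset. If late onset is counted from the last injection session, declare it as an added derivation, because the SAP counts from first injection; Protocol 8.6 has session dates recorded. The existing 120-day split from first injection would avoid the extra derivation.

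Narrowing SAP 3.2 alone, with a reason, would remove the contradiction but leave the question about lasting reactions without a planned answer.

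The cost is SAP wording, a few more tables and at most one small new derivation. No new data are needed.
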